3.2 Sample Size

The sample size is based on practical considerations. Approximately █ subjects will be enrolled. With at least 6 subjects receiving AMG 890 in each cohort, there is at least a 74% chance of detecting an adverse event with a true incidence of 20% within each cohort. With at least 10 subjects receiving both AMG 890 and statin, there is at least a 89% chance of detecting an adverse event with a true AE incidence rate of 20%. With █ subjects receiving AMG 890 there is a 95% chance of detecting an adverse event with a true incidence of 5%.

4. Covariates and Subgroups

4.1 Planned Covariates

Not applicable

4.2 Subgroups

No subgroup analysis is planned.

5. Definitions

Age at time of enrollment

Subject age in years at time of enrollment will be collected in the clinical database.

AUC_{last}

Area under the concentration-time curve from time zero to the last quantifiable concentration.

AUC_{inf}

Area under concentration-time curve from time 0 extrapolated to infinity.

Baseline

Baseline values for Lp(a) are defined as the mean of screening and day 1 predose. If for any reason only 1 value is available, then that value will be used as baseline.

For any other variable, unless otherwise specified, baseline is defined as the last assessment taken prior to administration of AMG 890 or placebo.

ECG Baseline value

Analysis of ECG is applicable to cohorts 1 to 5 and 8 and 9 only.

Baseline ECG for cohorts 1 to 5 is defined as the mean of the triplicate values measured on Day -1. Baseline ECG for cohorts 8 and 9 is defined as the mean of the 3 triplicate values measured at the Day -3 to -1 dosing pre check visit. If there are any missing values, the mean of the non-missing values will be taken as baseline.

Change from Baseline

Change from baseline is the arithmetic difference between post-baseline and baseline.

Enrollment Date

Enrollment date is defined as the date on which subject was enrolled in the study.

End of Study for the Overall Trial

Defined as when the last subject is assessed or receives an intervention for evaluation in the study i.e. last subject last visit, following any additional parts in the study (e.g. Follow-up period, long term follow-up) as applicable.

End of Study for Individual Subject

Defined as the last date recorded on the End of Study form for an individual subject.

End of Treatment Date

End of Treatment Date for cohort 1 and 2 is the date of Day 113 visit, for Cohort 3 to 7 is the date of Day 225 visit and for cohort 8 and 9 is the date of Day 365 visit.

Fridericia-corrected QT Interval (QTcF)

The Fridericia correction will be calculated from the investigator reported QT (msec) and RR interval (msec), as follows:

$$\text{QTcF} = \text{QT}/\text{RR}^{1/3}$$

Investigational Product

The term investigational product is used in reference to AMG 890 or placebo.

Percentage Change from Baseline

Percentage change from baseline is arithmetic difference between post baseline and baseline divided by baseline values times 100.

Randomization Date

Randomization date is defined as the date subject was allocated a unique randomization number and assigned to either AMG 890 or placebo group.

Study Day 1

defined as the first day that investigational product is administered to the subject.

Study Day

Post study day 1: study day= (date of event-study day 1) +1

Pre-study day 1: study day= (date of event-study day 1)

Treatment-emergent Adverse Event during Treatment Period

A treatment-emergent adverse event during treatment period is any adverse event starting on or after the first dose of investigational product (as determined by the flag indicating if the adverse event started prior to the first dose or not on the Adverse Events eCRF) and up to and including the End of Treatment Date, **or EOS date for subjects who early discontinue the study during the treatment period.**

Treatment-emergent Serious Adverse Event during Follow-up Period

Subjects in cohorts 1-7 will be followed up for SAE reporting (every 2 weeks for cohorts 1-2 and monthly for cohorts 3-7) if the Lp(a) level has not returned to $\geq 80\%$ of baseline by the end of treatment visit. SAEs during the follow-up period are defined as any serious adverse event **categorized as Adverse Events (AEs) starting on or after first dose of investigational product (as determined by “Did event start before first dose of investigational product” equal to No or missing on the Events eCRF) and starting on or after the end of treatment date and up to and including the end of study date for an individual subject.**

If end of treatment and end of study is same for a subject, then the subject will only have TEAEs for treatment period derived.

For subjects in Cohort 8 and 9 the end of treatment and end of study is same i.e. day 365 so for those cohorts only TEAEs for treatment period will be derived.

6. Analysis Sets

For all analyses, subjects will be analyzed according to the dose and treatment they received, not the dose and treatment to which they were randomized.

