and approved by the investigator, and acknowledged by the Amgen Medical Monitor. Written documentation of this review and Amgen acknowledgement is required for subject participation.

- **For cohort 9, medication used to manage diabetes not excluded by other exclusion criteria, provided subjects have been on a stable dose for at least 6 weeks prior to enrollment and plan to be on the same dose for the duration of the study. Medication must be reviewed and approved by the investigator, and acknowledged by the Amgen Medical Monitor. Written documentation of this review and Amgen acknowledgement is required for subject participation.**

220 Currently receiving apheresis as lipid reducing therapy

221 Subject has known sensitivity to any of the products or components to be administered during dosing

222 Has donated or lost  $\geq$  500 mL of blood or plasma within 60 days of day 1

223 A corrected QT interval (QTc) at screening of  $> 450$  msec in men or  $> 470$  msec in women or history of long QT syndrome

224 History of substance abuse within 12 months before screening

225 Positive test for drugs of abuse at screening or on day -1 for cohorts 1 to 5 or day -3 to -1 for cohorts 6 to 9

226 Use of nicotine or tobacco containing products (including but not limited to: snuff, chewing tobacco, cigars, cigarettes, electronic cigarettes, pipes, or nicotine patches) during the 6 months before screening

227 Unwilling or unable to abstain from nicotine or tobacco containing products (including but not limited to: snuff, chewing tobacco, cigars, cigarettes, electronic cigarettes, pipes, or nicotine patches) throughout the course of the study

228 Subject is unwilling or unable to limit alcohol consumption throughout the course of the study:

- Alcohol is prohibited 48 hours prior to admission to the research facility (day -1 for cohorts 1 to 5 and the sentinel pair of cohort 9; day 1 for cohorts 6 to 9 (other than the sentinel pair) and during the residency periods, and
- Alcohol consumption is limited to no more than 1 drink per day for females and 2 drinks per day for males for the duration of the study (1 drink is equivalent to 12 ounces of regular beer, 8 to 9 ounces of malt liquor, 5 ounces of wine or 1.5 ounces of 80 proof distilled spirits)

229 Subject will not be available for protocol-required study visits or procedures (including the research facility residency period), to the best of the subject's and investigator's knowledge

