### **13. STATISTICAL CONSIDERATIONS**

#### **13.1 Study Endpoints, Analysis Sets, and Covariates**

##### **13.1.1 Study Endpoints**

###### **13.1.1.1 Primary Endpoints**

- Subject incidence of treatment-emergent adverse events
- Safety laboratory analytes, vital signs, and electrocardiograms (ECGs)

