**13.5.2.1.3 Electrocardiogram**

For cohorts 1 to 5 and cohorts 8 and 9, summaries over time and/or changes from baseline over time will be provided for ECG parameters (eg, RR, PR, QRS, QTc). Subjects' maximum change from baseline in QTc will be categorized and the number and percentage of subjects in each group will be summarized. Subjects' maximum post-baseline values will also be categorized and the number and percentage of subjects in each group will be summarized. Baseline ECG recording is defined as the mean of the 3 sets of triplicate ECG results (a total of 9 assessments) at study day -1 for cohorts 1 to 5, and at the day -3 to -1 visit for cohorts 8 and 9.

For cohorts 6 and 7, the ECG measurements will be performed as per standard of care for routine safety monitoring, rather than for purposes of assessment of potential QTc effect. Since these evaluations may not necessarily be performed under the rigorous conditions expected to lead to meaningful evaluation of QTc data; summaries and statistical analyses of ECG measurements are not planned, and these data would not be expected to be useful for meta-analysis with data from other trials.

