9.6.5 Electrocardiogram

Each ECG will include following measurements: PR, QRS, QT, QTc, RR.

The following summary will be provided for cohorts 1 to 5 and Cohorts 8 and 9 only.

Summaries over time and change and percentage change from baseline over each scheduled time points (including time points with single and triplicate measurements) will be provided for each ECG parameter by treatment group and cohort.

Further subjects' maximum change from baseline in QTcF will be categorized in following categories and the number and percentage of subjects in each treatment group and cohort will be summarized. Unscheduled assessments will be included in the determination of the maximum change.

<=30 msec

>30-60 msec

>60 msec

Subjects' maximum post baseline values in QTcF will also be categorized in the following categories and the number and percentage of subjects in each treatment group and cohort will be summarized. Unscheduled assessments will be included in the determination of the maximum post baseline value.

<=450 msec

>450-480 msec

>480-500 msec

>500 msec

Subject level data listing will be reviewed.

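### The SAP's QTcF formula takes RR in msec without dividing by 1000, so every QTcF is 10 times too small and the two QTcF category tables cannot in practice show a prolongation

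*SAP*

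**What the plan says.** SAP Section 5 (Definitions, Fridericia-corrected QT Interval) gives both inputs in milliseconds: "The Fridericia correction will be calculated from the investigator reported QT (msec) and RR interval (msec), as follows". The formula printed beneath is QTcF = QT / RR^(1/3). Neither the SAP nor the protocol states that RR is converted to seconds. The protocol speaks only of QTc and names no correction method, so this is the only QTcF definition in the two documents.

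SAP Section 9.6.5 uses the derived value in two tables:

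- "Further subjects' maximum change from baseline in QTcF will be categorized in following categories": ≤30, >30–60 and >60 msec.
- "Subjects' maximum post baseline values in QTcF will also be categorized in the following categories": ≤450, >450–480, >480–500 and >500 msec.

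These tables carry out Protocol Section 13.5.2.1.3, which asks that the "maximum change from baseline in QTc will be categorized and the number and percentage of subjects in each group will be summarized" and makes a similar request for the maximum post-baseline value. On scope, SAP Section 5 says: "Analysis of ECG is applicable to cohorts 1 to 5 and 8 and 9 only". ECGs belong to the primary endpoint (Protocol Section 13.1.1.1): "Safety laboratory analytes, vital signs, and electrocardiograms (ECGs)".

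**The concern.** The formula and the bands are on different scales. Bands at 450 to 500 msec need QTcF in hundreds of msec. So does the protocol's exclusion criterion 223 on screening QTc, which is set at 450 msec for men and 470 msec for women. The printed formula returns values in tens of msec.

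If the derivation is programmed as written, the error runs in one direction: every subject moves towards the lowest band. The two tables are the SAP's only planned QTcF threshold analyses. They would show no prolongation for a first-in-human drug given at up to 675 mg, whatever its true effect within any plausible range. They would also waste the design effort in cohorts 1 to 5, 8 and 9, where nine baseline tracings and triplicate post-dose tracings are taken. Protocol Section 13.5.2.1.3 sets cohorts 6 and 7 apart, because their ECGs are not meant to assess a QTc effect.

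**Working it through.** The plan states no numerical QTcF result, so there is no figure to reproduce. The check compares the printed formula with the Fridericia form and then works back from the band limits.

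**Inputs from the documents.** QT and RR in msec and the printed formula (SAP Section 5); band limits (SAP Section 9.6.5); cohort sizes (SAP Table 1). The QT and RR values below are illustrative assumptions, as the documents give none.

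**Step 1: the factor.**

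- As printed: QT / RR^(1/3), RR in msec.
- Fridericia: QT / (RR/1000)^(1/3).
- Ratio: 1000^(1/3) = 10 for any QT and any RR.

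**Step 2: examples.**

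| QT (msec) | RR (msec) | As printed | RR in seconds | Value band as printed | Correct value band |
|---|---|---|---|---|---|
| 400 | 1000 | 40.0 | 400.0 | ≤450 | ≤450 |
| 400 | 800 | 43.1 | 430.9 | ≤450 | ≤450 |
| 520 | 1000 | 52.0 | 520.0 | ≤450 | >500 |
| 500 | 800 | 53.9 | 538.6 | ≤450 | >500 |

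Over QT 360 to 600 and RR 500 to 1500 msec, the printed formula gives values from 31.4 (QT 360, RR 1500) to 75.6 (QT 600, RR 500).

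For change, take a baseline of QT 400 at RR 1000. A rise to QT 520 at the same RR is a true change of 120 msec, in the >60 band. As printed it is 52.0 − 40.0 = 12.0, in the ≤30 band. A true rise of 70 msec appears as 7.

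**Step 3: what it takes to leave the lowest band.**

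- Value table: the printed QTcF exceeds 450 only if the true QTcF exceeds 450 × 10 = 4500 msec. In raw QT the limit is 450 × RR^(1/3): 3572 msec at RR 500, 3795 at RR 600, 4500 at RR 1000 and 5151 at RR 1500. Each is several times the RR interval itself.
- Change table: the printed change exceeds 30 only if the true change exceeds 30 × 10 = 300 msec. At constant RR, the raw QT rise must exceed 30 × RR^(1/3): 238 msec at RR 500, 300 at RR 1000 and 343 at RR 1500.

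**Step 4: subjects affected.** Cohorts 1 to 5, 8 and 9 are seven cohorts, each planned with 6 on AMG 890 and 2 on placebo: 7 × 6 = 42 plus 7 × 2 = 14, or 56 subjects.

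**Step 5: what is not affected.** QT, RR, PR and QRS do not use the formula. Percentage change in QTcF is unchanged because the factor cancels: from QT 400 to 520 at RR 1000 it is 30.0% either way. The screening QTc criterion is not tied to this definition.

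**The case against.** The best case on the other side accepts the arithmetic and disputes the consequence.

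- **The error might be caught.** SAP Section 9.6.5 also asks for over-time summaries and review of a subject listing, where a mean QTcF near 40 msec beside a mean QT near 400 would look odd. SAP Section 8.7 calls for output checks and for validated macros where these can produce the output. SAP Section 8.5 requires questionable values to be confirmed. The method is named and the limits show the intended scale, so a programmer might convert RR without being told. This makes silent failure less likely, but it does not correct the text. The documents do not show that a standard macro derives QTcF, and a check made against the SAP line would reproduce the error.
- **Other ECG information remains.** QT and RR are summarised, sites review every tracing, and the dose level review meetings see ECG data. This stands: the error is confined to derived QTcF values, their absolute changes and the two category tables.
- **The claim that no subject can leave the lowest band is too strong for the change table.** This also stands. A true rise above 300 msec would register, so the statement is practical rather than mathematical.
- **A division by 1000 could have been lost when the PDF was read.** This cannot be ruled out completely. However, the formula reads as complete, and the sentence before it separately puts RR in msec.

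**Conclusion.** The definition is wrong as written and should be corrected before the analysis is programmed or, if it already has been, before the output is relied on. The tenfold error is exact and does not depend on the example QT and RR values. Followed literally, the value table could register only a true QTcF above 4500 msec and the change table only a true rise above 300 msec. Both tables would therefore be uninformative for the 56 planned subjects and would err towards reassurance.

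Two conditions apply. The consequence assumes that the derivation follows the SAP line, and the documents do not show what was actually programmed. The count of 56 is the planned number in Table 1, before any expansion or replacement. The error does not reach the other ECG parameters, so the primary ECG endpoint as a whole is not lost. This is nonetheless a stated derivation rule for a primary safety endpoint that gives the wrong result.

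**What to change.** In SAP Section 5, replace the formula with QTcF = QT (msec) / [RR (msec)/1000]^(1/3), or keep the printed form and state that RR is in seconds. Leave the band limits in SAP Section 9.6.5 unchanged. Check the derivation program against the corrected line with a simple test: QT 400 at RR 1000 must return 400, and QT 500 at RR 800 must return 538.6.

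The cost is one line of SAP text and one check of the program. It needs no protocol amendment, no new data and no change to any clinical rule.

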## **12.        SAFETY DATA COLLECTION, RECORDING, AND REPORTING**

### **12.1        Definition of Safety Events**

#### **12.1.1        Adverse Events**

An adverse event is defined as any untoward medical occurrence in a clinical trial subject. The event does not necessarily have a causal relationship with study treatment. The investigator is responsible for ensuring that any adverse events observed by the investigator or reported by the subject are recorded in the subject's medical record.

The definition of adverse events includes worsening of a pre-existing medical condition. Worsening indicates that the pre-existing medical condition or underlying disease (eg, diabetes, migraine headaches, gout) has increased in severity, frequency, and/or duration more than would be expected and/or has an association with a significantly worse outcome than expected. A pre-existing condition that has not worsened more than anticipated (ie, more than usual fluctuation of disease) during the study, or involves an intervention such as elective cosmetic surgery or a medical procedure while on study, is not considered an adverse event. Abnormal laboratory findings without clinical significance are usually not considered adverse events. However, laboratory value changes that require treatment or adjustment in current therapy may be considered adverse events.

The investigator's clinical judgment is used to determine whether a subject is to be removed from treatment due to an adverse event. In the event a subject, or subject's legally acceptable representative requests to withdraw from protocol-required therapies or the study due to an adverse event, refer to Section [11.1](#) for additional instructions on the procedures recommended for safe withdrawal from protocol-required therapies or the study.

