## 12.2 Safety Event Reporting Procedures

### 12.2.1 Adverse Events

#### 12.2.1.1 Reporting Procedures for Adverse Events That do not Meet Serious Criteria

The investigator is responsible for ensuring that all adverse events observed by the investigator or reported by the subject that occur after the first dose of investigational product through the end of treatment visit are reported using the Event eCRF.

The investigator must assign the following adverse event attributes:

- Adverse event diagnosis or syndrome(s), if known (if not known, signs or symptoms),
- **Did the event start prior to the first dose of investigational product,**
- **Assessment of seriousness,**
- Dates of onset and resolution (if resolved),
- Severity,
- Assessment of relatedness to investigational product, protocol required therapies, and/or study mandated procedures
- Action taken, **and**
- **Outcome of event.**

The adverse event grading scale used will be the Amgen Standard Adverse Event Grading Scale: mild (aware of sign or symptom, but easily tolerated), moderate (discomfort enough to cause interference with usual activity), and severe (incapacitating with inability to work or do usual activity). The grading scale used in this study is described in the [Appendix A](#).

The investigator must assess whether the adverse event is possibly related to the investigational product (AMG 890 or placebo). Relatedness means that there are facts or reasons to support a relationship between investigational product and the event.

The investigator must assess whether the adverse event is possibly related to any study mandated activity (eg, administration of investigational product, protocol-required therapies, use of medical device(s) and/or procedure (including any screening procedure(s)).

The investigator is responsible for reviewing laboratory test results and determining whether an abnormal value in an individual study subject represents a clinically significant change from the subject's baseline values. In general, abnormal laboratory findings without clinical significance (based on the Investigator's judgment) are not to be recorded as adverse events. However, laboratory value changes that require treatment

or adjustment in current therapy are considered adverse events. Where applicable and preferentially, clinical sequelae (not the laboratory abnormality) are to be recorded as the adverse event.

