#### Serious Adverse Event Diagnosis or Syndrome\* –

- If the diagnosis is known, it should be entered. Do not list all signs/symptoms if they are included in the diagnosis.
- If a diagnosis is not known, the relevant signs/symptoms meeting serious criteria should be entered.
- If the event is fatal, the cause of death should be entered and autopsy results should be submitted, when available. Do not enter "Death," as this is an outcome, not an event.

**Date Started\*** – Enter date the adverse event first started rather than the date of diagnosis or hospitalization. For serious events, the start date is the date the event started, not the date on which the event met serious criteria. This is a mandatory field.

**Date Ended** – Enter date the adverse event ended. For serious events, this is not the date when the event no longer met serious criteria. If the event has not ended at the time of the initial report, a follow-up report should be completed when the end date is known. If the event is fatal/resulted in death, enter the date of death as the end date

If event occurred before the first dose of investigational product, add a check mark in the corresponding box.

**Serious Criteria Code\*** - This is a mandatory field for serious events – Enter reason why the reported event has met serious criteria:

- Immediately life-threatening – Use only if the subject was at immediate risk of death from the event as it occurred. Emergency treatment is often required to sustain life in this situation.
- If the investigator decides an event should be reported in an expedited manner, but it does not meet other serious criteria, "Other medically important serious event" may be the appropriate serious criterion.

**Relationship to IP\*** – The Investigator must determine and enter the relationship of the event to the IP at the time the event is initially reported. This is a mandatory field.

**Relationship to Amgen device\*** – The Investigator must determine and enter the relationship of the event to the Amgen device (eg, prefilled syringe, auto-injector) at the time the event is initially reported. If the study involves an Amgen device, this is a mandatory field. This question does not apply to non-Amgen devices used in the study (eg, heating pads, infusion pumps)

**Outcome of Event\*** – Enter the code for the outcome of the event at the time the form is completed. This is a mandatory field.

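### Treatment emergence rests on an onset flag alone, so an event that begins in screening and turns serious after dosing leaves the primary TEAE tables, and post-dose worsening may do so too

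*SAP*

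**What the plan says.** The first primary endpoint in Protocol 13.1.1.1 is "Subject incidence of treatment-emergent adverse events". SAP Section 5 defines such an event in the treatment period as "any adverse event starting on or after the first dose of investigational product (as determined by the flag indicating if" it began before dosing, up to the end of treatment date or, after early discontinuation, the end of study date. That is the whole test. SAP Section 10 declares no departure from the protocol on this point.

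The flag is an attribute the investigator must assign on the Event eCRF (Protocol 12.2.1.1): "Did the event start prior to the first dose of investigational product".

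Three other places bear on how it is answered:

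- Protocol Appendix B, item 3: "For serious events, the start date is the date the event started, not the date on which the event met serious criteria". A box is ticked when the event predates the first dose.
- Protocol 12.1.1: "The definition of adverse events includes worsening of a pre-existing medical condition", meaning that the condition "has increased in severity, frequency, and/or duration more than would be expected" or has a significantly worse outcome than expected.
- SAP Section 5, serious events in follow-up: these qualify when the flag is "equal to No or missing on the Events eCRF". The treatment-period definition does not mention a missing flag.

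Non-serious events are collected only if they are ones "that occur after the first dose of investigational product through the end of treatment visit are reported using the Event eCRF" (Protocol 12.2.1.1). Serious events are collected from consent (Protocol 12.2.1.2).

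**The concern.** A safety count in a dose-escalation study should include harm that appears after dosing, whether it is a new event or an old one that becomes worse or serious. The SAP asks only when the event began. The protocol's start-date rule for serious events points to the earliest date, so the two rules together can classify a post-dose serious deterioration as not treatment-emergent.

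The affected tables are the main safety summaries in SAP 9.6.1: incidence by treatment group and cohort, tabulation by system organ class and preferred term, and severity. Any loss makes the drug look better tolerated, which is also the direction of the study hypothesis. Cohorts 6 to 9 allow stable medication for chronic conditions, and cohort 9, at the highest dose, also admits controlled diabetes. Worsening of an existing condition is therefore a foreseeable event in this study.

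**Working it through.** **Step 1. Put cases through the rules as written.**

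- *A. A complaint begins, non-serious, in the 28-day screening window and leads to admission after dosing.* It is not collected while non-serious and before dosing. On admission it becomes a reportable serious event. Appendix B sets its start date at the first onset and its pre-dose box is ticked. The literal answer to the eCRF flag is Yes. The SAP definition fails, so the event is absent from the TEAE summaries. It remains in the listing of serious events in SAP 9.6.1.
- *B. A stable condition in the medical history worsens after dosing.* Under Protocol 12.1.1 the worsening is the adverse event. If the flag is answered for the worsening, it is No and the event counts. If it is answered for the underlying condition, it is Yes and the event is dropped. No passage in either document says which is meant.
- *C. The flag is blank.* In follow-up the event counts. In the treatment period the SAP does not say. SAP Appendix A imputes start dates, but the definition reads the flag, so the imputation does not settle the matter.

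Case A follows from stated rules. Case B depends on site practice. Case C is a gap in wording.

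One reading is assumed for case A: that the serious-event summary for the treatment period in SAP 9.6.1 is limited to treatment-emergent events, as the wording around it suggests.

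**Step 2. Check the plan's own detection figures (SAP 3.2).** The chance of at least one event is 1 − (1 − p)^n.

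- n = 6, p = 0.20: 1 − 0.80^6 = 0.738 (stated 74%).
- n = 10, p = 0.20: 1 − 0.80^10 = 0.893 (stated 89%).
- p = 0.05, n blacked out. Table 1 gives 5 × 6 + 9 + 9 + 6 + 6 = 60 on AMG 890, so 1 − 0.95^60 = 0.954 (stated 95%).

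All three reproduce. None of them measures the loss at issue, because the documents give no rate at which events would be flagged as pre-dose.

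**Step 3. Size of one misclassified subject.**

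- AMG 890 group of 6 (cohorts 1 to 5, 8 and 9): 1/6 = 16.7 percentage points.
- AMG 890 group of 9 (cohorts 6 and 7): 1/9 = 11.1 points.
- Pooled placebo, cohorts 1 to 5 (5 × 2 = 10) or cohorts 6 to 9 (3 + 3 + 2 + 2 = 10): 1/10 = 10.0 points.

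Each figure assumes that the subject has no other event counted in the same row.

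**The case against.** The strongest reply is that the protocol already deals with worsening. Under 12.1.1 a stable condition is not an adverse event, and its worsening is. The event then starts at the worsening, the flag is properly No, and the SAP rule captures it. This stands in large part. A reader might infer that the SAP removes every worsened pre-existing condition, above all in cohort 9; the documents do not support that, because nothing tells sites to flag a worsening as pre-dose. What remains is that nothing tells them the opposite either.

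A second reply concerns Appendix B. Its preamble lists the fields on which the paper form must agree with the events CRF: term, serious criteria and relationship. Start date and the pre-dose box are not listed, so it would be too strong to say that the paper form forces the eCRF answer. Still, Protocol 12.2.1.2 asks in general terms for consistency with the Event eCRF, and the flag question, read literally, gets the same answer.

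Third, case A is narrow. Exclusion criterion 205 keeps out disorders judged to pose a risk. The event would be reported to the sponsor within 24 hours and reviewed in listings, and the medical monitor is unblinded throughout. Fasting glucose and other laboratory values are assessed separately under the primary endpoint. All of this stands: the event is not lost to safety oversight. It is lost to the incidence tables, which are what the primary endpoint reports.

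Finally, the rule applies alike to AMG 890 and placebo. That is true, but incidence is described cohort by cohort, and an undercount in both arms is still an undercount.

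**Conclusion.** The point holds in a limited form. For events that begin in screening and first become serious after dosing, the SAP definition and the Appendix B start-date rule together give a wrong count in the primary TEAE and treatment-period serious-event tables. For post-dose worsening of a pre-existing condition, loss is possible and depends on how the flag is understood.

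The bias is downward and its size cannot be stated. Events of the first kind are probably few; a single one is 16.7 points in a six-subject group. A reader might go further and discount the 74% and 95% detection figures by some assumed share of lost events. The documents give no such share, and those figures concern seeing an event at all, which a listing still allows. A reader might also infer that a missing flag is excluded in the treatment period; the definition is silent and does not say so.

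This should be corrected before the primary analysis, because the change is cheap and the endpoint is primary.

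**What to change.** 1. In SAP Section 5, keep the present onset rule and add that an event or condition present before the first dose is also treatment-emergent if, from the first dose onward, it worsens as Protocol 12.1.1 defines worsening, including the requirement that the change exceed what would be expected, or first meets a serious criterion. Assign it to the treatment or follow-up period by the date of worsening or of becoming serious.
2. In the eCRF guideline, state that a post-dose worsening is entered as a new event and that the flag is answered for the worsening. Reconcile this with the start-date rule in Protocol Appendix B, for example by keeping the original onset on the serious-event form and recording the date of becoming serious separately.
3. Count a missing flag as No in the treatment period, as in follow-up, unless a complete start date shows onset before dosing.

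The cost is SAP and guideline wording and some programming. Cohorts 1 to 8 are closed to enrolment, so some existing records may need a query to obtain the date of worsening or of becoming serious. A few ordinary fluctuations of chronic conditions may be counted, under the same rule in both arms; the Protocol 12.1.1 threshold limits this.
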